7.6.11. Electrocardiogram

A 12-lead resting ECG will be obtained during the Screening Visit, and at study Visits 2, 3, 4, and 7/EOS/ET Visits. As applicable, ECGs will be conducted pre-dose, within 60 minutes of study drug application. All ECGs will be reviewed by a central reader (Cardiologist). The cardiologist will interpret, sign, and date the ECGs. Clinical interpretations will be recorded in the CRF (normal or abnormal with specific abnormality noted).

Note: one ECG to be collected prior to starting treatment (Screening or Visit 2), provided that ECG is normal or has a finding that is not clinically significant.

7.6.12. Investigator Skin Assessment Examination

At the Screening Visit and Day 1 (prior to dosing), the upper arms/shoulders will be examined to determine there is no skin disease or condition, including eczema, psoriasis, melanoma, acne, contact dermatitis, scarring, imperfections, lesions, tattoos, or discoloration that may affect treatment application, application site assessments, or affect absorption of the study drug where study drug will be applied.

7.6.13. Investigator Skin Irritation Examination

The investigator will conduct a skin irritation examination pre-dose of the application site(s) at Week 6, Week 14, and Week 38 EOS/ET, and Unscheduled Visits. In addition, parents/caregivers will be asked about skin irritation at the Week 10 Telephone Follow-up call. When excessive skin redness is noted, efforts will be made to temporarily apply the gel to a non-red area of the upper arms/shoulders and/or right/left thighs at the approval of the investigator. The investigator will use discretion in suspending dosing for patients with a skin redness score of '4' (intense erythema) but will in all score of '4' cases immediately (within 24 hours) complete an adverse event report and contact their study CRA and the Sponsor Medical Monitor.

Application of ZYN002 to the right or left thigh should be viewed as a temporary alternate application site only until the redness on the upper arms/shoulders is reduced.

Patients having a skin irritation score > '0' at Week 38 will continue to be followed through Unscheduled Visits until the skin irritation score is recorded as '0' (no erythema). At this time, the patient will be discharged from the study.

Refer to [Table 7](#) for the Skin Irritation Scale to be used for skin redness examinations.

Table 7: Skin Irritation Scale

| Score | Definition |
|-------|--|
| 0 | No erythema |
| 1 | Minimal erythema |
| 2 | Moderate erythema with sharply defined borders |
| 3 | Intense erythema with or without edema |
| 4 | Intense erythema with edema and blistering/erosion |

A de-identified picture of an application site may be taken at the discretion of the Principal Investigator.

Should the patient experience dry skin at the application sites, moisturizing lotion (Cetaphil) which will be supplied by the Sponsor, may be applied two hours post gel application.

7.6.14. Patient Skin Irritation Diary

Parents/caregivers will be instructed on completion of the daily skin irritation diary at Day 1 (Section 20.2). Parent/caregiver scoring of skin irritation will start the evening of Day 1 (PM application) and will continue daily through discharge of the study. Before each evening dose, parents/caregivers will record the skin score in their daily skin irritation diary. When skin redness is noted, patients should apply the gel to a non-red area of the upper arms/shoulders and/or right and left thighs. If the skin irritation score is higher than '2' (moderate erythema) the parent/caregiver will contact the study site to determine if an *Unscheduled Visit* is required.

Application of ZYN002 to the right or left thigh should be viewed as a temporary alternate application site only until the redness on the upper arms/shoulders is reduced.

The investigator will use discretion in suspending dosing for patients with skin check score of '4' but will in all cases of a score of '4' immediately (within 24 hours) complete an adverse event report and contact their study CRA and the Sponsor Medical Monitor.

The patient's skin check diary will be reviewed by the investigator at Week 6, Week 14, and Week 38 EOS/ET Visit, and *Unscheduled Visits*.

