Patients should keep the application site dry for six hours but may apply an approved moisturizing lotion (Cetaphil), provided by the Sponsor, two hours after dosing. The application site should be covered to minimize sun exposure when going outside during the day. Sunscreen at the application site may be used two hours after dosing. If excessive skin irritation occurs at the application site, the parent (after consultation with the Investigator) may switch the application site temporarily to the upper thighs.

Patients who weigh ≤ 35 kg will receive 125 mg CBD Q12H (every 12 hours) (± 2 hours); for a total daily dose of 250 mg CBD. Patients who weigh > 35 kg will receive 250 mg CBD Q12H (± 2 hours); for a total daily dose of 500 mg CBD. All patients will remain on their assigned dose through Week 6. At Week 6, if the patient has less than a 25% improvement from baseline in the ABC-C irritability subscale, the investigator may increase the dose, as follows:

- Patients who weigh ≤ 35 kg receiving a total daily dose of 250 mg CBD may increase to a daily dose of 500 mg.
Patients who weigh > 35 kg receiving a daily dose of 500 mg CBD may increase the dose to 750 mg/day.

The following questionnaires and scales will be administered at Visit 2, Visit 3, Visit 4, Visit 5, Visit 6, and Visit 7 EOS/ET, unless an exception is noted:

- ABC-C
- CGI-S
- Clinical Global Impression-Improvement (CGI-I) (not completed on Visit 2, Day 1)
- ADAMS
- C-SSRS
- Qualitative Caregiver Reported Behavioral Problems Survey (not completed at Visit 2)
- Children's Sleep Habit Questionnaire (Visit 4 and Visit 7 EOS/ET only)
- PARS-R

End of Study (EOS) / Early Termination Visit (ET):

Patients not on AEDs who are prematurely discontinued or do not qualify for Period 2, will complete the early termination procedures at Visit 4 EOS/ET.

Patients taking valproate or valproic acid for the treatment of seizures or epilepsy, including patients who prematurely discontinue, will taper their current study dose in the following manner beginning at Visit 7 EOS/ET. Should patients taking AEDs at the EOS continue to receive drug through Special Access (if available) they will not taper their dose.

- Participants who weigh 35 kg or less and were receiving 250 mg daily dose of ZYN002, will be reduced to 125 mg daily dose over one week. Only one sachet will be applied each day around the same time in the evening. After the taper, the participants will discontinue from the study at Week 40.

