Patient safety will be monitored at each study visit using standard measures, including physical and neurological exams, examination of skin at application sites for irritation, vital signs (including oral, infrared forehead or tympanic temperature), 12-lead ECGs, the C-SSRS, safety laboratory tests (Screening, Week 6, Week 14, and Week 38), urinalysis (Screening, Week 6, Week 14, and Week 38), and AE monitoring.

In addition, there will be a follow-up telephone visit at Week 10 for patients who had their dose adjusted at Week 6.

At Screening, patients will have an epilepsy diagnosis confirmed by the Investigator, if applicable. The parents/caregivers of patients with a current epilepsy and/or seizure diagnosis will be asked at each study visit if there has been any increase in frequency or severity of the patient's seizures. If an increase in frequency or severity is noted, this will be recorded as an adverse event (AE) in the case report form (CRF).

Parents/caregivers will be provided a diary to complete a daily skin irritation examination. Every evening from Day 1 through discharge from the study, parent/caregivers will record the skin irritation score in the daily skin irritation diary. When skin redness is noted, parents/caregivers should apply the gel to a non-red area of the upper arms and shoulders. If the skin irritation score is higher than '2' (moderate erythema) at any time, the parent/caregiver will contact the study site to determine if an Unscheduled Visit is required.

The Investigator will use discretion in suspending dosing for patients with a skin irritation score of '4' but will, in all cases, immediately (within 24 hours) complete an adverse event report and contact their study Clinical Research Associate (CRA) and the Zynerva Medical Monitor. A de-identified photograph of the skin irritation (or area) of interest may be taken after consultation with and approval of the Sponsor. Digital photographs will be retained for information purposes only. In place of suspending the dosing due to skin irritation, the Investigator may instruct the parent/caregiver to temporarily change the application site to the upper thigh.

Plasma Samples for CBD, THC and Valproic Acid:

Blood samples for plasma levels of CBD and THC will be collected at Screening (Visit 1 baseline), Week 6/Visit 3, Week 14/Visit 4, and Week 38/Visit 7 EOS/ET.

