Patients and parents/caregivers will be required to visit the clinic at Day 1/Visit 2, Week 6/Visit 3, and Week 14/Visit 4 End of Study (EOS)/Early Termination (ET), for the collection of: vital signs, ECG, concomitant medication review, physical and neurological exam, pregnancy tests, skin assessment examination (Day 1) and skin irritation examination (Visit 3 and 4), adverse AE review, and questionnaire’s and scale completion. Blood samples for laboratory tests, CBD/THC PK exposure, and valproic acid (for patients taking valproate or valproic acid) levels will be collected at Week 6/Visit 3 Week 14/Visit 4, and Week 38/Visit 7 EOS/ET.

In addition, there will be a follow-up telephone visit at Week 10 for patients who had their dose adjusted at Week 6. Patients that complete Visit 4 and have made a $\geq 35\%$ improvement on the ABC C irritability subscale will be allowed to continue to Period 2 for an addition 24 weeks of treatment. Period 2 will have additional Visits at Week 22/Visit 5, Week 30/Visit 6, and Week 38/Visit 7 EOS/ET. Refer to the Schedule of Assessments (Table 5 and Table 6) for the activities to be completed at each study Visit.

Note: only one ECG to be collected prior to starting treatment (Screening or Visit 2), provided that ECG is normal or has a finding that is not clinically significant.

At Visit 2, parents/caregivers will be instructed on proper application of the study drug (Section [20.1](#)). Patients will be permitted to shower or clean the arm area up to 30 minutes prior to the study dose.

Parents/caregivers will use gloves supplied by the Sponsor to apply the study drug. Parents/caregivers will apply all study drug to clean, dry, intact skin, thoroughly massaging it

into the right and/or left upper arms and shoulders until the area is dry. The study drug will be rubbed in completely and must be dry prior to dressing.

Patients should keep the application site dry for six hours but may apply an approved moisturizing lotion (Cetaphil), provided by the Sponsor, two hours after dosing. The application site should be covered to minimize sun exposure when going outside during the day. If redness occurs at the application site, the parent (after consultation with the Investigator) may switch the application site temporarily to the upper thighs. The following questionnaires and scales will be administered at Visit 2, Visit 3, Visit 4, Visit 5, Visit 6, and Visit 7 EOS/ET:

- ABC-C
- CGI-S

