- h. At Weeks 6, and 14 parents/caregivers will administer the dose in the clinic after they have their PK and valproic acid (for patients taking valproate/valproic acid) blood drawn. At Week 14 patients who require a tapering period will be provided a 1 or 2-week supply of study treatment.
- i. A skin assessment examination will be completed by the Investigator at Day 1 pre-dose. Shoulders and upper arms will be examined to determine there are no skin disease or condition, including eczema, psoriasis, melanoma, acne, contact dermatitis, scarring, imperfections, lesions, tattoos, or discoloration that may affect treatment application, application site assessments, or affect absorption of the study drug where study drug could be applied.
- j. Parents/caregivers will assess the application site daily and record all irritation scores in their daily skin irritation diary, starting with the PM dose on Day 1. When irritation exists, efforts will be made to apply the gel to a non-irritated area of the upper arms/shoulders and/or right and left upper thighs. Temporary application to the upper thighs can only be used after consultation with the investigator. If the skin irritation score is greater than "2", the patient will contact the Investigator to determine if an Unscheduled Visit is required.
- k. The investigator will perform a skin irritation examination pre-dose at study Visits 3, Visit 4/EOS/ET and Unscheduled Visits. The parent/caregiver will also be asked about the patients skin irritation at the Week 10 Telephone Follow-up call.
- l. A Telephone Follow-Up will occur for those patients whose dose was increased at Week 6.

Table 6: Period 2 Schedule of Assessments – 24-Week Extension Treatment

| Study Procedures | 24-Week Treatment Period 2 Visit Schedule | | | Taper Period, If Applicable | | Study Visit Week 40 or Week 41 for AED Patients Tapering Study Drug ^a | Un-scheduled Visit(s) |
|---|--|--------------------------------------|---|--|---------------------------|---|--------------------------|
| | Visit 5 Week 22 (± 3 days) | Visit 6 Week 30 (± 3 days) | Visit 7 Week 38 EOS/ET ^a (± 3 days) | Week 39 (± 3 days) | Week 40 (± 3 days) | | |
| | Study Drug Dosing | | | Tapered 50% each week. No Study Visit | | | |
| Concomitant Medications | X | X | X | | | X | X |
| Physical/Neurological Exam ^b | | | X | | | X | |
| Vital Signs ^c | X | X | X | | | X | X |
| 12-lead ECG | | | X | | | | |
| Laboratory Tests and Urinalysis | | | X | | | | |

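### Protocol 7.6.14 omits the investigator consultation required elsewhere before gel goes on the thighs; separately, SAP 8.1.9 leaves thigh scores out of the investigator irritation summary

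*Protocol*

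**What the plan says.** Protocol 7.6.14 (Patient Skin Irritation Diary) instructs: "When skin redness is noted, patients should apply the gel to a non-red area of the upper arms/shoulders and/or right and left thighs". It adds that the thigh is only a temporary alternative until the arm redness settles. It asks the caregiver to contact the site when the score exceeds 2, so that the site can decide on an Unscheduled Visit. It does not mention consultation or approval before the thighs are used.

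Six other Protocol places do:

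- Synopsis, application paragraph: "If excessive skin irritation occurs at the application site, the parent (after consultation with the Investigator) may switch the application site temporarily", the destination being the upper thighs.
- 7.6.1.1: "If redness occurs at the application site, the parent (after consultation with the Investigator) may switch the application site temporarily to the upper thighs".
- 10.5 (Administration): the same rule as 7.6.1.1.
- Table 5 footnote j and Table 6 footnote h: "Temporary application to the upper thighs can only be used after consultation with the investigator".
- 7.6.13 (Investigator Skin Irritation Examination): "a non-red area of the upper arms/shoulders and/or right/left thighs at the approval of the investigator".

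The matching redness sentence in the Synopsis under Safety Monitoring does not offer the thighs at all: "When skin redness is noted, parents/caregivers should apply the gel to a non-red area of the upper arms and shoulders".

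On measurement, Protocol 7.6.13 has the investigator examine the application site or sites before dosing at Weeks 6, 14 and 38 and at Unscheduled Visits. Protocol 13.5 summarises application site irritation by score with no body-site limit. SAP 8.1.9 names only the left and right shoulder and upper arm, and the corresponding output is Table 14.3.8.2. SAP section 10 reports no changes from the protocol.

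**The concern.** Safety and tolerability are the primary objective, and local irritation is a scored part of tolerability. Two separate gaps touch it.

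The first is in conduct. Section 7.6.14 governs what families do each evening. Followed as written, it lets a caregiver move gel to a child's thighs at a score of 1 or 2 without telling the site, and the first scheduled diary review is at Week 6. The dedicated skin assessment before treatment covers only the arms: "the upper arms/shoulders will be examined to determine there is no skin disease or condition". Consultation is therefore the only thigh-specific check in the plan, and this section leaves it out.

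The second is in reporting. If the investigator scores thigh skin, the summary specified in SAP 8.1.9 has no place for the result. A table meant to describe local tolerability would then leave out the children whose arms reacted enough to need a change of site.

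**Working it through.** No plan figure is in dispute. The check compares texts, followed by a rough size.

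**Step 1. Thigh use and the investigator step**

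| Protocol location | Thighs offered? | Investigator step |
|---|---|---|
| Synopsis, application paragraph | Yes | Consultation |
| 7.6.1.1 | Yes | Consultation |
| Table 5 footnote j | Yes | Consultation |
| Table 6 footnote h | Yes | Consultation |
| 10.5 | Yes | Consultation |
| 7.6.13 | Yes | Approval |
| 7.6.14 | Yes | None stated |
| Synopsis, Safety Monitoring (redness sentence) | No | Not applicable |
| 9.1 | Yes, as product description | None stated |

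That is 5 consultation + 1 approval = 6 places with the step. The SAP repeats the consultation rule three times, in its synopsis and its two schedule footnotes. Section 9.1 describes permitted sites and is not a caregiver instruction, so 7.6.14 is the one operative instruction without the step. Footnotes j and h carry nearly the same sentence as 7.6.14 and then add the consultation rule, which suggests that 7.6.14 is a shortened copy.

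**Step 2. Where an investigator-rated thigh score would go**

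- Score 1, 2 or 3: not recorded as an adverse event (Protocol 11.2.1.1), not among the SAP 8.1.9 sites, but available for Listing 16.12.2.
- Score 4: also recorded as an adverse event and reported within 24 hours.
- Other application-site signs or symptoms on the thigh: recorded as adverse events (11.2.1.1).
- Caregiver diary scores: SAP 8.1.8 summarises them with no site restriction, so they are counted, though not separated by site.

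The reporting gap is therefore confined to investigator scores below 4.

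**Step 3. Size**

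The nearest in-document figure is in Protocol 5.3.2. In the 12-week Fragile X study, one of 20 enrolled children had the site changed to the thighs for 6 days.

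- Proportion: 1/20 = 5%.
- Exact (Clopper-Pearson) 95% limits: the 0.025 quantile of Beta(1, 20) = 0.0013 and the 0.975 quantile of Beta(2, 19) = 0.2487, so 0.1% to 24.9%.
- Applied to 20 children here: 20 × 0.0013 = 0.03 to 20 × 0.2487 = 4.97, or about 0 to 5 children.
- Period 1 lasts 14 × 7 = 98 days, with scheduled examinations at about Day 42 and Day 98. A 6-day switch covers an examination if it starts on that day or in the 5 days before, which gives 6 + 6 = 12 start days. If all 98 start days are equally likely, 12/98 = 0.122.
- Expected scheduled Period 1 examinations with a thigh site in use: 1 × 0.122 = 0.12 for one child and 5 × 0.122 = 0.61 for five.

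This assumes that all 20 children complete Period 1 with visits on nominal days and one switch per affected child. Week 38 and Unscheduled Visits are not counted. The documents give no figure for switches made without consultation, so the conduct gap cannot be sized.

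**The case against.** The strongest reply is that the rule is already clear. It appears six times in the Protocol, including the Administration section and the section immediately before 7.6.14, and both schedule footnotes make it a strict condition. Site staff read the whole protocol. Families receive the application instructions and the diary, which are attachments not shown here and may already require a call. The reporting half depends on a case report form that is also not shown: if it has no thigh field, there is nothing to tabulate. The title of Table 14.3.8.2 has no site limit, and SAP section 9 lists all data collected.

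Most of this stands as a limit on importance. It does not remove the omission from the section that governs daily practice, nor the mismatch between SAP 8.1.9 and Protocol 7.6.13 and 13.5.

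A reader might go further in four ways that the documents do not support:

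- That thigh skin goes unchecked before treatment. Exclusion criterion 20 covers skin conditions without limiting them to the arms, and complete physical examinations take place at Screening and Day 1 (7.6.9).
- That 7.6.14 permits lasting thigh use. It says the thigh is temporary.
- That the thigh is an untested site. A 14-day study in 39 healthy subjects included it among three application sites (5.3.1).
- That children were in fact switched without supervision, or that thigh reactions are lost. Nothing shows the first. Step 2 shows that thigh scores, if recorded, remain in a listing and that a score of 4 is an adverse event.

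**Conclusion.** Both gaps are in the text, and both are minor. Section 7.6.14 lacks the consultation or approval that six other Protocol places require. SAP 8.1.9 covers fewer sites than Protocol 7.6.13 and 13.5, so an investigator-rated thigh score of 1 to 3 would be listed but not summarised.

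The expected effect on the investigator table is below one scheduled Period 1 examination: about 0.1 with one child affected and about 0.6 with five. This rests on carrying over one switch from a different population under a different rule. In that study the switch followed a rash for which drug was withheld for a day; it was not a caregiver's response to redness. No conclusion about efficacy, sample size or overall safety changes. The point is worth correcting because it concerns a safety instruction for children and the repair is small.

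**What to change.** 1. In Protocol 7.6.14, make the thigh option conditional on prior consultation with the investigator. Nothing else in that sentence needs to change: the section already says thigh use is temporary, and a fixed arms-first order would go beyond the either-or wording of 7.6.13 and the footnotes.
2. In SAP 8.1.9 and Table 14.3.8.2, summarise the investigator score for all application sites in use, with a thigh row wherever the case report form records a thigh score.
3. Check that the application instructions and diary given to families state the consultation rule.

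Cost: the first change is one clause, but Protocol 16.1 requires ethics committee approval of amendments, so it should travel with another amendment. The second is one table row if the thigh is already a recorded site; if it is not, a footnote saying so is enough. The Note to File at the front of the SAP, effective 16 February 2026, says the Protocol and SAP will not be updated. If conduct is complete, the first change is useful only for later protocols, while any recorded thigh scores can still be tabulated or footnoted in the report.

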7.6.15. Clinical Laboratory Testing

All blood samples will be collected and handled in accordance with the instructions from the local laboratory. For collection of laboratory samples, patients should fast for approximately four to eight hours prior to having blood drawn for blood laboratory analysis. Instructions regarding the collection, processing, and shipping of these samples will be provided by the laboratory chosen for this study.

All abnormal laboratory test results will be followed to a satisfactory resolution.

Samples will be collected based on Table 4, Table 5 and Table 6 Schedule of Assessments. Routine laboratory tests (clinical chemistry, hematology, and urinalysis) will be collected at the Screening Visit, Week 6, Week 14, and Week 38 EOS/ET Visits.

